**Version History:**

Version Number/Date	Change
0.1 18Jul2014	-
0.2 29Aug204	Incorporated comments from DE and circulated for wider review
0.3 06Oct2014	Incorporated changes following ST meeting 17Sep2014
0.4 21Oct2014	Incorporated changes following email to ST 06Oct2014
1.0 25Nov2014	Finalised version 1.0
1.1 18Jan2017	Updated to reflect revised bacteriology algorithm; changed INH-mono resistant patients to be classified as late exclusions; other minor clarifications; updated names for signature on front page

## 1. Introduction

This document outlines the efficacy statistical analysis plan (SAP) for the protocol STAND, a phase 3 trial of three experimental regimens of the combination regimen of moxifloxacin, PA-824 and pyrazinamide (MPaZ).

The primary efficacy analysis will be conducted using culture results from liquid culture (MGIT) and will evaluate the hypothesis that in the patients with drug-sensitive tuberculosis (DS-TB) treated with any of the experimental MPaZ regimens, the incidence of bacteriologic failure or relapse or clinical failure at 12 months from the start of therapy is non-inferior to the proportion observed in patients who are treated with the 6 month standard isoniazid, rifampicin, pyrazinamide, ethambutol (HRZE/HR) regimen.

The three experimental regimens detailed below will be compared to the control regimen in the order specified. For the second and third comparison, statistical inference will only be made if non-inferiority is declared on the preceding comparison:

*First comparison:* MPaZ with 200mg PA-824 (MPa200Z) for 6 months vs HRZE/HR

*Second comparison:* MPaZ with 200mg PA-824 (MPa200Z) for 4 months vs HRZE/HR

*Third comparison:* MPaZ with 100mg PA-824 (MPa100Z) for 4 months vs HRZE/HR

300 patients per randomised arm will be recruited. See Appendix 1 for details of the sample size. An additional non-randomised group of up to 300 patients with multi-drug resistant (MDR) TB will be treated with regimen MPa200Z for 6 months. No formal statistical analysis is planned for this group and unless otherwise stated all analyses outlined in this document refer to the analysis of the 4 randomised groups of the DS-TB patients.

While STAND is an open label study, only members of the Data Safety Monitoring Committee (DSMC) and the unblinded statistician(s) will have access to data **grouped by study arm**. Access to data by investigators, CRO and TB Alliance staff will not allow any access to data grouped by study arm. In addition, site staff will be strongly discouraged from attempting to aggregate by treatment arm at a site level.

## 2. Primary Efficacy Endpoint

The primary efficacy endpoint will be the incidence of bacteriologic failure or relapse or clinical failure within 12 months from start of therapy. See section 6 for the detailed definition of an “unfavourable response” at 12 months.

There will be three main analyses of the primary efficacy endpoint: A per-protocol (PP) analysis, a modified intent to treat (MITT) analysis and an intent to treat (ITT) analysis. As the true bacteriologic treatment failure and relapse rate in the control group is expected to be between 3% and 5%, “unfavourable” rates in any defined ‘ITT’ population will likely be increased considerably by factors other than bacteriologic or clinical treatment failure and relapse. The PP and MITT analyses will be considered primary; results of ITT and additional sensitivity analyses (listed in section 8) will need to be consistent to draw a strong conclusion.

### 3. Definitions and data handling issues

#### 3.1. Definitions

**Positive culture** refers to the culture being positive for M.tb. N.B.: In the absence of the speciation data, the unconfirmed result will be treated as positive for M.tb. False positive or contaminated will be treated as missing. Specimens classified as non-tuberculous mycobacteria (NTM) and negative for M.tb will be treated as contaminated (adequate conditions for growth of M.tb exist if NTM grow). The bacteriology algorithm for reporting MGIT results can be found in STAND Laboratory Manual. Two sputum samples per visit are collected at each visit throughout treatment and follow-up. The culture result for a given visit is established using all samples obtained for that visit. A positive culture takes precedence over a negative culture at the same visit.

**Culture negative status** is achieved when a patient produces at least 2 negative culture results at different visits (at least 7 days apart) without an intervening positive culture result for M.tb. The date of the first negative culture of these two is the date at which culture negative status was obtained. Once obtained, culture negative status continues until there are two positive cultures at different visits (at least 7 days apart), without an intervening negative culture, or until there is a single positive culture not followed by two negative cultures. Culture negative status can be achieved at any time during treatment or follow-up but before any re-treatment and can be re-established.

Patients with two contaminated or missing samples at a given visit (from Month 2 onwards) will be asked to return to produce two more sputum samples. A single culture result or inability to produce sputum (see section 3.2) at 12 months will be sufficient to count that patient as having data for primary endpoint classification.

**Treatment failure or Bacteriologic failure** is defined as being declared an unfavourable status (as defined in section 6) at or before the end of treatment (either 4 or 6 months) or failing to attain culture negative status and being declared an unfavourable outcome.

**Relapse or Bacteriologic relapse** is defined as failing to maintain culture negative status or being declared an unfavourable outcome after the end of treatment (either 4 or 6 months) in those patients who attained culture negative status by the end of treatment, and were re-infected with the **same** (as per the STAND Laboratory Manual) *Mycobacterium tuberculosis (MTB)* strain.

**Reinfection or Bacteriologic Reinfection** is defined as failing to maintain culture negative status or being declared an unfavourable outcome after the end of treatment (either 4 or 6 months) in those patients who attained culture negative status by the end of treatment and were infected with a *Mycobacterium tuberculosis (MTB)* strain that is **different** (as per the STAND Laboratory Manual) from the infecting strain at baseline.

**Clinical failure** is defined as a change from protocol-specified TB treatment or retreatment for TB during follow up as determined by the treating physician, or TB-related death.

The **treatment period** is defined as either 4 or 6 months from start of therapy depending on allocated treatment regimen and the **follow-up period** is defined as the period after the end of treatment to the end of follow-up.

### 3.2. Inability to produce sputum

In general, inability to produce sputum is treated as being equivalent to having a negative (favourable) culture result. This includes the rare situation where a patient who never achieves culture negative status due to inability to produce sputum, after TB confirmation via culture has been confirmed on the applicable baseline sample, but completes 12/24 months follow-up without clinical or microbiological evidence of relapse. Such a patient will be considered to have a favourable outcome.

### 3.3. Isolated positive cultures

It is known that occasionally patients produce sputum samples that are isolated positives, that is a positive result preceded by a series of negative cultures and followed thereafter by at least 2 negative cultures without an intervening positive result. This phenomenon may be the result of a sealed cavity breaking down or laboratory contamination and does not in itself signify that the patient is relapsing. In the event of a single positive culture result occurring in a patient who has previously been classified as having culture negative status (in the absence of any retreatment), the patient will not be classified as a recurrence unless a second positive culture result is obtained at a separate visit (at least 7 days apart) without an intervening negative culture or unless the patient is lost to follow up or completes the study (and is unable to be brought back) before two negative cultures are obtained. The clinical condition of the patient will also be taken into account in deciding whether re-treatment is indicated.

Most of the experience with isolated positives has been with solid culture. Because liquid culture is more sensitive, it is possible that more than one isolated positive may occasionally occur. Therefore, the clinical condition of the patient will also be taken into account when deciding whether re-treatment is indicated and in determining the outcome. For example, if a patient after being culture negative has two positive cultures in a row, but is deemed to be doing well clinically, the investigator may choose to leave the patient untreated on clinical grounds. In such a case, so long as two consecutive negative cultures are eventually obtained in the absence of treatment, the patient will not be classified as a recurrence.

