### **6.1.3. Unfavourable status in MITT population**

1. Patients not classified as having achieved or maintained culture negative status when last seen, or
2. Patients previously classified as having culture negative status who, following the end of treatment, have two positive cultures without an intervening negative culture, (however, see Section 3.3 for an exception), or
3. Patients who had a positive culture not followed by at least two negative cultures when last seen, or
4. Patients dying from any cause during treatment, except from violent or accidental cause (e.g. road traffic accident), not including suicide (eg, suicide will be considered an unfavourable outcome) or
5. Patients definitely or possibly dying from TB related cause during the follow-up phase or
6. Patients requiring an extension of their treatment beyond that permitted by the protocol, a restart or a change of treatment for any reason except reinfection or pregnancy, or
7. Patients failing to complete an adequate course of treatment, as defined in section 4.5, who were unassessable at 12 months, or
8. Patients lost to follow up or withdrawn from the study before the end of treatment

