## **8. Sensitivity analyses of primary endpoint analysis**

In addition to analysing the primary endpoint data by per protocol and MITT and ITT, it is planned to conduct the following sensitivity analyses:

1. An analysis of all randomised patients
2. An analysis of the ITT population, with missing outcomes data treated as unfavourable
3. An analysis of the ITT population, with missing outcomes data treated as favourable

4. An analysis of the ITT population, with missing outcomes data treated according to status at the last observation (last two samples)
5. An analysis of patients in the MITT and PP populations where reinfections are classified as unfavourable outcomes
6. An analysis of the MITT and PP populations treating all deaths as unfavourable
7. An analysis of the MITT population in which patients who changed treatment for reasons other than failure or relapse were classified according to their status at the end of follow-up.

In these sensitivity analyses, reinfections are considered as missing outcome data (except for point 5).

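### The Section 3.3 exception lets an open-label re-treatment decision help settle the outcome after two consecutive post-treatment positives, and no Section 8 analysis tests that dependence

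*SAP*

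**What the plan says.** **Culture status.** SAP Section 3.1 sets the general rule: "Once obtained, culture negative status continues until there are two positive cultures at different visits (at least 7 days apart), without an intervening negative culture". It adds that the status can be regained, provided no re-treatment has been given.

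**The exception.** Section 3.3 notes that liquid culture is more sensitive than solid culture, so more than one isolated positive may occur. It therefore has clinical condition taken into account "when deciding whether re-treatment is indicated and in determining the outcome". Its example is a patient with two positives in a row who is doing well: "the investigator may choose to leave the patient untreated on clinical grounds", and "so long as two consecutive negative cultures are eventually obtained in the absence of treatment, the patient will not be classified as a recurrence".

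**Import into the primary analyses.** MITT item 6.1.3(2) makes unfavourable those previously culture-negative patients who, after the end of treatment, "have two positive cultures without an intervening negative culture, (however, see Section 3.3 for an exception"). PP item 6.1.4(2) has the same wording. Section 7 names PP and MITT as primary.

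**The other branch.** Under 6.1.3(6), MITT counts as unfavourable "a restart or a change of treatment for any reason except reinfection or pregnancy". Under 6.1.4(6), PP does the same for a restart or change prompted by an unfavourable outcome, whether or not bacteriology confirms it.

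**Blinding.** The Introduction begins the relevant paragraph "While STAND is an open label study, only members of the Data Safety Monitoring Committee" and restricts access to data grouped by arm. It does not hide an individual patient's regimen from the treating investigator.

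**The concern.** After two consecutive post-treatment positives, the outcome depends partly on a choice made by someone who knows the regimen. If the patient is re-treated, the outcome is unfavourable in both primary analyses. If the patient is left untreated and two negatives follow, the outcome can be favourable. Relapse after treatment is a central way in which a shorter regimen could fail, so these are endpoint-relevant patients. If investigators used the exception at different rates by arm, the risk difference would shift for reasons unrelated to efficacy.

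The weakness is not that the exception exists. The plan offers no analysis showing whether the conclusion depends on it, and no count showing how often it was used. This matters because Section 7 asks for consistent sensitivity results before non-inferiority is declared.

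**Working it through.** **1. Does any planned analysis remove the exception?**

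| Place in SAP | What it varies or shows | Removes the exception? |
|---|---|---|
| Section 8, item 1 | Population (all randomised) | No |
| Section 8, items 2–4 | Handling of missing outcomes in ITT | No |
| Section 8, item 5 | Reinfections | No |
| Section 8, item 6 | Deaths | No |
| Section 8, item 7 | Treatment changed for reasons other than failure or relapse | No; these patients were not left untreated |
| ITT (6.1.1, 6.1.2) | Anyone not favourable is unfavourable, but favourable has one definition for all analyses | No |
| Section 9.3 | Time to event on the same PP, MITT and ITT classifications | No |
| Section 12 | Reasons in patients judged to have failed or relapsed | No; patients spared by the exception do not appear |

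Section 4.6 specifies review blind to arm for cause of death. Nothing similar is specified for Section 3.3.

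**2. The plan's own sample size, as a check on the inputs.** Appendix 1 gives 16% unfavourable, a 12-point margin, one-sided 2.5%, 90% power, 15% unassessable and 8% isoniazid mono-resistant.

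n = 2 × 0.16 × 0.84 × (1.960 + 1.282)² / 0.12² = 196.1 assessable per arm.

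196.1 / (1 − 0.15 − 0.08) = 254.7, which gives the stated 255.

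**3. Weight of one patient.** With the 300 per arm actually planned, 300 × 0.77 = 231 assessable (an assumption built from the Appendix 1 rates). One reclassified patient moves the difference by 1/231 = 0.43 points.

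**4. Where a borderline result turns.** Take 37/231 unfavourable in control (16.0%) and the unadjusted interval d + 1.96 × √[p₁(1 − p₁)/231 + p₀(1 − p₀)/231].

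- 48/231: d = 4.76 points, upper bound 11.8%, non-inferior.
- 49/231: d = 5.19 points, upper bound 12.3%, not non-inferior.

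The primary analysis is stratified by HIV status and cavitation, so its interval would differ somewhat.

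**5. Illustration of a differential effect.** Assume 231 per arm, control 16% and a true experimental rate of 28%, exactly at the margin. Suppose a share m of the experimental arm only is moved to favourable although truly unfavourable. The chance of declaring non-inferiority is Φ(m/SE − 1.96), with SE computed at 28% − m and 16%.

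| m | Patients | Chance of declaring non-inferiority |
|---|---|---|
| 0 | 0 | 2.5% |
| 0.5% | 1.2 | 3.4% |
| 1% | 2.3 | 4.5% |
| 2% | 4.6 | 7.7% |
| 3% | 6.9 | 12.4% |

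Every m is an assumption, as is placing all such patients in one arm. The same movement in the control arm alone would act the other way.

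**The case against.** The best defence is that this is a pre-specified rule with a stated bacteriological reason, named in both places that use it. Most of that defence stands, and it disposes of several stronger readings that a reader might infer.

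- **That Section 3.3 contradicts Section 3.1.** It does not. Section 3.1 says when culture negative status ends, not that the outcome is then unfavourable, and it allows the status to be re-established. The unfavourable label comes from 6.1.3(2) and 6.1.4(2), which cite the exception.
- **That the investigator's decision alone makes the outcome favourable.** It does not. Two consecutive negatives without treatment must follow. A patient left untreated who stays positive is unfavourable under items 1 and 3 of 6.1.3 and 6.1.4.
- **That the exception has no time limit.** Section 3.3 sets none, but 6.1.1 requires negative status at weeks 50 to 54 and at least two negatives after the last positive. For the primary endpoint this largely bounds it.
- **That the bias favours the experimental arms.** Nothing in the SAP shows this. Greater caution with a new or shorter regimen could produce more re-treatment there and push the other way.

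It is also fair to say that open-label judgement enters elsewhere. Section 3.1 defines clinical failure by the treating physician's decision, and 6.1.4(6) accepts clinical grounds alone. An analysis without the exception would not remove those. Further, 0.43 points is the weight of any one patient under any rule.

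The objection does not reach the gap in Section 8. Withholding data grouped by arm does not blind the individual decision. The component parts that Section 7 says will be weighed are components of the unfavourable rate, so patients spared by the exception are not among them.

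**Conclusion.** The point holds as a limited one. In both primary analyses, classification after two consecutive post-treatment positives depends partly on an open-label re-treatment decision, and neither ITT nor any Section 8 analysis tests that dependence. The SAP expects more than one isolated positive only occasionally and gives no rate, so the size and direction of any bias cannot be derived from it.

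What can be said is conditional. At an assumed 231 assessable per arm, each reclassified patient is worth about 0.43 points, and one patient separates upper bounds of 11.8% and 12.3% in a borderline result. The error rates in the illustration show what an assumed one-sided use of the exception would do; they do not predict that it will happen. This is a cheap improvement to the plan, not a flaw that invalidates the endpoint.

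**What to change.** Add one item to Section 8, for MITT and PP. Two positive cultures at least 7 days apart, without an intervening negative, occurring after the end of treatment in a patient with culture negative status, count as unfavourable regardless of the re-treatment decision or later negatives. Reinfections are handled as in the primary analysis.

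The restriction to the period after the end of treatment matches 6.1.3(2) and 6.1.4(2). Without it, on-treatment reversions that later clear would be counted too, and the analysis would no longer isolate the exception.

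Report by arm, alongside it, the number of patients classified under the Section 3.3 exception. If that number is small and similar across arms, the question is largely answered.

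**Cost.** One more analysis, from cultures already collected. Rates may be slightly higher, because some true isolated positives will be counted as unfavourable. The primary rule, sample size and patient management do not change.

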### 3.4. Timing of events

In all analyses, visit date rather than day or week number will be used to define the timing of events. The 4 month regimens will be taken as 17 weeks (119 days) and the 6 month regimens as 26 weeks (182 days) from the start of therapy. For the end of treatment visit (months 4/6), a  $\pm 1$  week window will be applied (as per the protocol). For the 12 and 24 month visits, a window of  $\pm 2$  weeks will be applied (as per the protocol).

## 4. Analysis populations

The analysis populations for efficacy analyses are:

- The **All Randomised** population defined as all patients randomised with no exclusions
- The **Intent to treat (ITT)** population is defined as All Randomised excluding late screening failures (see 4.1)
- The **Modified intent to treat (MITT)** population is defined as the ITT population with extra exclusions (See 4.2)
- The **Per-protocol (PP)** population is defined as the MITT population with extra exclusions (see 4.3)

#### **4.1. Exclusions from ITT analysis (late screening failures)**

1. Patients randomised into one of the DS arm who on subsequent receipt of the results of the MGIT drug sensitivity tests are found to be rifampicin and/or pyrazinamide and/or fluoroquinolone resistant and/or INH mono-resistant) documented from Day 1 (baseline) sputum samples (or screening or out to Week 4 if the baseline is contaminated or negative) (late exclusions from the study). These patients will be withdrawn from the study.
2. Patients without culture confirmation of M. tb at Day 1 (baseline) sputum samples (or screening or out to Week 4 if the baseline is contaminated or negative) (late exclusions from the study)
3. Patients withdrawn from treatment because of a protocol violation at enrolment (late exclusions from the study, based on data collected prior to randomisation).

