## **5. Baseline comparisons of key characteristics**

The following baseline characteristics of patients on each of the five study arms (including the non-randomised MDR group) will be tabulated and compared for each analysis population: age, gender, race, region, site, smoking status, HIV status/CD4 count, cavitation (based on blinded, central assessment of the chest radiograph (refer to Central Chest X-ray Manual), initial bacterial load in sputum as indicated by baseline Time to Positivity (TTP) result from MGIT, resistance to first and second line antibiotics and whether or not the patient is taking efavirenz.

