#### Details of sample size and issues relating to choice of delta, the non-inferiority margin

The following assumptions have been made in calculating the numbers of subjects needed for the primary endpoint analysis.

- The unfavorable rate in the control regimen will be 16%, consistent with the control arm unfavourable rate in a recent Phase 3 TB trial.
- An unassessable rate of 15%, consistent with the overall unassessable rate in a recent Phase 3 TB trial.
- An additional 8% excluded for isoniazid mono-resistance, consistent with the overall percentage observed in a recent Phase 3 TB trial.
- An acceptable non-inferiority margin (delta) is 12% (see below)
- The power to demonstrate non-inferiority is 90% and the significance is 2.5% (1-sided).

Under these assumptions we would require 255 subjects for each treatment arm, giving a total sample size of 1,020 DS-TB subjects. Although these are considered to be reasonable assumptions based on recent data, in order to allow for the possibility of higher unfavorable and/or unassessable rates, or somewhat greater than 8% of subjects with INH mono-resistance, 300 DS-TB subjects will be recruited to each randomized arm giving a total of 1,200 subjects with DS-TB. Note that the primary analysis of the DS-TB subjects will exclude the subjects with isoniazid mono-resistance.

Examples of maximum observed effects which still meet the 12% margin for non-inferiority are given in Table A1 below for varying levels of the number N assessable and the proportion unfavourable in the control arm. Scenarios with observed differences of 6% or more are considered highly unlikely given the sample size for STAND is based on an expected MITT control arm unfavorable rate of 16% based on a recently completed phase 3 efficacy trial.

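### Section 4.1(1) excludes isoniazid resistance only when it is 'mono', so isoniazid-plus-ethambutol resistance, read literally, stays in ITT and MITT (and by default PP), where it is expected to handicap only the control arm

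*SAP*

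**What the plan says.** SAP Section 4.1, item 1, lists the drug-resistance results that make a randomised DS-TB patient a late exclusion: "rifampicin and/or pyrazinamide and/or fluoroquinolone resistant and/or INH mono-resistant". They are read from baseline sputum, with screening or early samples as back-up. The item ends by saying that these patients leave the study. Ethambutol is not on the list, and the SAP nowhere defines mono-resistance.

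Appendix 1 uses the same term twice: in the sample-size assumptions ("An additional 8% excluded for isoniazid mono-resistance") and in a closing note ("Note that the primary analysis of the DS-TB subjects will exclude the subjects with isoniazid mono-resistance"). The version history records that version 1.1 made INH-mono-resistant patients late exclusions.

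Section 4 builds ITT by removing the Section 4.1 exclusions from all randomised patients. MITT is a subset of ITT, and PP a subset of MITT.

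Section 1 states the hypothesis for drug-sensitive TB. It names the control as the "6 month standard isoniazid, rifampicin, pyrazinamide, ethambutol (HRZE/HR) regimen" and the experimental combination as moxifloxacin, PA-824 and pyrazinamide. Section 5 tabulates "resistance to first and second line antibiotics" by arm in each analysis population.

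**The concern.** The list treats isoniazid differently from the other drugs. Resistance to rifampicin, pyrazinamide or a fluoroquinolone excludes a patient whatever else the isolate resists. Resistance to isoniazid excludes only if it stands alone. A patient resistant to one control drug is removed, while a patient resistant to that drug and to a second control drug is kept. The SAP gives no reason for this.

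The direction matters in a non-inferiority trial. The retained resistance concerns drugs found only in the control regimen, and the one control arm serves all three comparisons. Any extra control failures raise the rate against which each experimental arm is judged, for a reason unrelated to how the regimens perform in drug-sensitive disease. The effect is that of a slightly wider margin.

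**Working it through.** **1. Which isoniazid-resistant isolates leave under the literal wording**

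| Baseline resistance | Criterion met in 4.1(1) | In ITT? |
|---|---|---|
| Isoniazid alone | INH mono-resistant | No |
| Isoniazid + rifampicin | rifampicin | No |
| Isoniazid + pyrazinamide | pyrazinamide | No |
| Isoniazid + fluoroquinolone | fluoroquinolone | No |
| Isoniazid + ethambutol (or another unlisted drug) | none | Yes |

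**2. Whether a later rule removes them**

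- MITT (Section 4.2): no item concerns resistance, so they stay.
- PP (Section 4.3): no item names resistance. Item 2 removes a patient whose treatment was modified for a reason other than poor response, unless already unfavourable. A change made because of a resistance result would fit that item. Without such a change the patient stays.
- MITT outcome (Section 6.1.3, item 6): a change of treatment for any reason but reinfection or pregnancy is unfavourable. A change prompted by the resistance result would therefore count as a failure in MITT, while the same patient leaves PP. A mono-resistant patient would be in neither population.

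**3. The plan's own sample size**

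Inputs from Appendix 1: 16% unfavourable in the control arm (taken as equal in both arms), margin 12 points, one-sided 2.5%, power 90%, 15% unassessable, 8% isoniazid mono-resistant.

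n = 2 × 0.16 × 0.84 × (1.960 + 1.282)² / 0.12² = 196.1 assessable per arm.

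196.1 / (1 − 0.15 − 0.08) = 196.1 / 0.77 = 254.7, i.e. 255. The stated figure reproduces. With 300 recruited, 300 × 0.77 = 231 per arm are analysed.

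**4. Size of the bias**

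Let f be the share of retained isoniazid-plus-other resistant patients in the analysed control arm, and e their excess unfavourable risk on HRZE/HR. The SAP gives neither, so both are assumptions. The experimental arms are taken as unaffected.

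Shift in control rate = f × e.

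For type I error, set the true rates in the remaining patients at the margin, 28% against 16%, with 231 per arm. The control rate becomes 0.16 + f·e, and

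SE = √{[0.28 × 0.72 + (0.16 + f·e)(0.84 − f·e)] / 231},

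type I error = Φ(f·e / SE − 1.96).

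| f | e | Shift (points) | Extra control failures in 231 | One-sided type I error |
|---|---|---|---|---|
| 0 | – | 0 | 0 | 2.5% |
| 1% | 10 points | 0.1 | 0.23 | 2.7% |
| 1% | 30 points | 0.3 | 0.69 | 3.0% |
| 3% | 10 points | 0.3 | 0.69 | 3.0% |
| 3% | 30 points | 0.9 | 2.08 | 4.2% |

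Worked top row of the range: f·e = 0.009; SE = √{(0.2016 + 0.1404) / 231} = 0.0385; 0.009 / 0.0385 = 0.234; Φ(−1.726) = 4.2%.

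Outside that range, f = 0.25% with e = 10 points gives a 0.03-point shift and an error still at about 2.5%. With f = 3% and e = 50 points the shift is 1.5 points and the error 5.8%.

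**The case against.** **The term may already mean what is wanted.** Because rifampicin, pyrazinamide and fluoroquinolone resistance are listed beside it, mono-resistant could be read as isoniazid resistance without those three. On that reading the gap closes. This stands as a caveat: using the term again in Appendix 1 and the version history does not define it. But two readings that give different primary populations are themselves a reason to fix the wording.

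**The effect is small and assumed.** This stands. With 16% in both arms and 231 per arm, the standard error of the difference is √(2 × 0.1344 / 231) = 3.4 points. The largest shift in the assumed range, 0.9 points, is about a quarter of that. The assumed prevalence also pools all unlisted partner drugs, while the loss of a second control drug applies only to ethambutol.

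**The retained patients would be visible.** Section 5 tabulates resistance by arm and population. That makes any imbalance in the count apparent, but it does not take these patients out of the primary estimate.

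**Stronger readings that the document does not support.** A reader might infer that Section 4.1(1) removes only isoniazid mono-resistant patients. It does not: three other resistances are listed, and the gap is confined to isoniazid combined with an unlisted drug. A reader might also infer that these patients always remain in PP, but Section 4.3 item 2 can remove them. Nor is the bias certain to favour the experimental arms in the realised data. The direction is an expectation that rests on a positive excess risk in the control arm, and with a handful of patients per arm chance could reverse it.

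**Conclusion.** The point holds on the literal wording. The isoniazid criterion is narrower than the others without a stated reason, and it leaves isoniazid-plus-ethambutol resistance in ITT and MITT, and in PP by default. The expected bias is towards non-inferiority in all three comparisons.

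Its size rests wholly on assumed prevalence and excess risk. Over the range taken here it equals at most about two extra control failures in 231. That would not decide the trial unless a result lay near the margin, a situation for which Section 7 itself makes provision. A reader might conclude that the sample size is wrong; it is not, since 255 reproduces. The point deserves correction because the effect is systematic, its expected direction is anti-conservative, and it is cheap to remove.

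**What to change.** For the analysis populations, define the Section 4.1(1) isoniazid criterion as baseline isoniazid resistance with or without resistance to any other drug. Apply it identically in all four randomised arms, from the same baseline drug-sensitivity results (and the same back-up samples) as the other criteria. Align the Appendix 1 note. If the team already intends this, a definition of the term is enough. The wording should be settled before data are seen by arm.

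Item 1 of Section 4.1 ties the same list to withdrawal from the study. Whether these patients are also withdrawn is a clinical-management matter. The sponsor should reconcile that sentence with the analysis definition; no withdrawal rule is proposed here.

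The cost is a few more exclusions. At the assumed 1% to 3%, that is 3 to 9 of 300 per arm. Even at 3%, 300 × (1 − 0.15 − 0.08 − 0.03) = 222 remain per arm, above the 197 (196.1 rounded up) needed. Appendix 1 already gives a rate of isoniazid mono-resistance above 8% as one reason for recruiting 300 and not 255. No new data are needed, because Section 5 already tabulates the resistance results.
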